6.6.2 Dietary Restrictions

6.6.2.1 Confinement Period

A standard diet will be designed by a dietician. For each meal, the caloric and fat content should be controlled in order to avoid “high-fat” diet. The FDA guidance on food-effect studies for bioequivalency testing identifies a “high-fat” diet as a diet which maintains approximatively 50 percent of total caloric content of the meal and is high in calories (approximately 800 to 1000 calories) (FDA, 2002).

In order to avoid any effect on assessment of BoExp, grilled or pan-fried meat, smoked pre-cooked meats (e.g., tuna, ham, corned beef, and meats), smoked bacon and sausage will not be permitted (Tiffany et al., 1991). In addition, to avoid any effect on the measurement of CYP1A2 activity, alcohol, broccoli, brussels sprouts, cauliflower, grapefruit, and xanthine-containing foods and beverages (coffee, tea, chocolate, cocoa, mate, guarana etc.) will be forbidden (Faber et al., 2004) (except for the intake of the caffeine tablet for CYP1A2 measurement). Consumption of quinine-containing drinks (e.g., tonic water) is not allowed.

Subjects are not allowed to bring their own food or beverages to the investigational site. Meals will be served according to the schedules provided in Section 9. Additional light snack, fruits, and raw vegetables can be distributed to the subjects without restrictions at any time during confinement as long as they fulfill the above requirements described in this section. Consumption of water is allowed as desired. The same menu and meal schedule will be administered uniformly for all subjects in all study arms. In addition for the purpose of the Ames test planned on Day 0 and Day 5, the menus served on Day-1 and Day 4 will be identical.

Fasting state has to be observed for at least 10 hours prior to blood draws for:

1. safety laboratory on screening, Day 0, Day 6
2. risk marker in serum/plasma/blood on Day 0 and Day 6.
3. serum/plasma bio-banking samples for further analysis of BoExp and risk markers at the Screening Visit, on Day 0, Day 6.
4. blood bio-banking for transcriptomics on Day 0, Day 6.

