6.6.2.2 Ambulatory Period

The above dietary restrictions are not applicable for the ambulatory period. However, 3 days prior to the Day 30 Visit, the Day 60 Visit, and the Day 90 Visit, and during visits on site, subjects will be asked by the study collaborators to refrain from consuming grapefruit or grapefruit-containing products, or quinine-containing drinks (e.g., tonic water). Alcohol, broccoli, brussels sprouts, cauliflower, chargrilled meat, xanthine-containing foods and beverages (e.g., coffee, tea, chocolate, cocoa, mate, guarana) will not be allowed on site during the ambulatory visits.

A fasting state has to be observed for at least 10 hours prior to blood draws for:

1. safety laboratory on Day 31, Day 61, and Day 91
2. risk factor assessments in serum/plasma/blood on Day 31, Day 61 and Day 91.
3. serum/plasma bio-banking samples for further analysis of BoExp and risk markers on Day 91.
4. blood bio-banking for transcriptomics on Day 91.

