**Table 18. Time Schedule – Day 90 Visit (08:00 AM of Day 90 to time of discharge of Day 91)**

Time	Blood sample	Procedures	Additional information
		Start of procedure	Day 90
08.00 AM		Opening of the Visit	No product restriction prior to the opening of the visit Product use will be allowed on site in the THS 2.2 Menthol and mCC arms from 08:00 AM to 11:00 PM
		AE/SAE questioning; Concomitant medication	The use of THS 2.2 Menthol in smokers allocated to mCC and SA arms will be forbidden
		Support for smoking cessation (SA arm only) if needed	At any time during the day
08:30 AM-09:30 AM		Start of HST recording for 4 hours	At any time of the day
09:00 AM ± 20 min		Start of collection of 24-hour urine to Day 90 sampling bottle	In the THS 2.2 Menthol and mCC arms, the HST SODIM® device has to be used for all smoking events, if compatible mCCs are smoked
Before 10:00 AM		Breakfast with a caffeine tablet containing approximately 170 mg of caffeine + 150 ml water ± 10 ml	HST recording will be done only on the subject's assigned product
10:00 AM-12:30 PM		CO breath test	The subject must empty his bladder and discard the urine prior to starting urine collection
10:00 AM-12:30 PM	√	COHb in blood	The time of the tablet intake must be recorded
10:00 AM-12:30 PM	√	Nicotine, cotinine in plasma	Irrespective of the time of product use
12:30 PM-01:30 PM		End of collection HST recording	Irrespective of the time of product use
Before 02:30 PM		Lunch	One blood sample will be drawn, irrespective of the time of product use
			The HST should be recorded over a period of 4 hours ± 15 minutes

Data and information contained in this document are considered to constitute trade secrets and confidential commercial information, and the legal protections provided to such trade secrets and confidential information are hereby claimed under the provisions of applicable law. No part of this document may be publicly disclosed without the written consent of Philip Morris Products S.A.

Time	Blood sample	Procedures	Additional information
Start of procedure		Day 90	
03:00 PM-04:00 PM	√	CYP1A2 activity in plasma	6 hours ±15 minutes after intake of the caffeine tablet
08:00 PM-09:30 PM		HST questionnaire (THS 2.2 Menthol and mCC arms only)	If compatible mCC are smoked
08:00 PM-11:00 PM		Fagerström Test for Nicotine Dependence (FTND)	
08:00 PM-11:00 PM		MCEQ (THS 2.2 Menthol and mCC arms, only)	
08:00 PM-11:00 PM		QSU-brief questionnaire	
In the evening before 09:00 PM		Dinner	

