12.6.2.4 CYP1A2 Activity

CYP1A2 activity will be measured in plasma on Day 0, Day 5 and Day 90. In this study the CYP1A2 activity will be calculated using the molar ratio of PX and CAF, as described in Section 7.1.3 "CYP1A2". Descriptive statistics of the values and percent change on Days 5 and 90 from Baseline and supportive listings will be provided.

The analysis will compare the log-transformed Day 5 values between the THS 2.2 Menthol and mCC arms and between the THS 2.2 Menthol and SA arms. ANCOVA models will be used on CYP1A2 activity levels with terms for log-transformed baseline, sex, average daily mCC consumption over the last 4 weeks as reported during screening and randomization arm. No adjustment will be made for multiple comparisons. If the results from the Day 5 analysis are significant (one-sided p-value ≤ 0.025) then the statistical significance will be repeated for the analysis at the Day 90 values. The SAS code will be similar to that described in Section 12.6.1.3 "Sensitivity Analysis".

Geometric LS means for each product along with the ratio (THS 2.2 Menthol :mCC) and 95% CI will be presented in the tables.

CYP1A2 activity will also be examined to compare the observed reductions in THS 2.2 Menthol vs. SA using the same methodology as above.

If there are any CYP1A2 assessments performed within 5 half-lives since the use of a concomitant medication affecting CYP1A2 activity, the analysis will be repeated by excluding these assessments for both the PP Set and FAS

All summaries and analyses will be performed on the FAS, and PP Set.

The data will be presented in the below outputs:

TFL number	Title
TABLES	
15.2.4.23.1	Descriptive Statistics of CYP1A2 Activity (%) – PP Set
15.2.4.23.2	Descriptive Statistics of CYP1A2 Activity (%) – FAS

TFL number	Title
15.2.4.24.1	Analysis of CYP1A2 Activity (%) – PP Set
15.2.4.24.2	Analysis of CYP1A2 Activity (%) – FAS
LISTINGS	
15.3.3.5	Listing of CYP1A2 Activity and Changes from Baseline

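### Dietary caffeine is barred before the Day 0 and Day 5 CYP1A2 tests but allowed at home until Day 90 check-in, so the Day 90 PX/CAF ratio is not comparable and the arm contrast may be biased

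*Protocol*

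**What the plan says.** Protocol 6.6.2.1 (confinement) states that "xanthine-containing foods and beverages (coffee, tea, chocolate, cocoa, mate, guarana etc.) will be forbidden", apart from the test tablet. The reason given is "to avoid any effect on the measurement of CYP1A2 activity". Alcohol, broccoli, brussels sprouts, cauliflower and grapefruit are restricted for the same reason.

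Protocol 6.6.2.2 then says: "The above dietary restrictions are not applicable for the ambulatory period". For the three days before each ambulatory visit, subjects are asked only to "refrain from consuming grapefruit or grapefruit-containing products, or quinine-containing drinks". For caffeine the rule is that "xanthine-containing foods and beverages (e.g., coffee, tea, chocolate, cocoa, mate, guarana) will not be allowed on site during the ambulatory visits".

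Protocol 7.5.2.2 bases CYP1A2 activity on plasma PX and CAF about six hours after one caffeine tablet. It schedules no sample before the tablet. On Day 90 subjects check in at about 08:00 (Protocol 4.1). Table 18 lists "Breakfast with a caffeine tablet containing approximately 170 mg of caffeine", before 10:00, with the blood draw six hours later.

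SAP 12.6.2.4 fits an ANCOVA on the log ratio with log baseline as a covariate, and evaluates Day 90 significance only if Day 5 is significant. Its one repeat analysis begins "If there are any CYP1A2 assessments performed within 5 half-lives since the use of a concomitant medication affecting CYP1A2 activity". Dietary caffeine has no counterpart.

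**The concern.** The sponsor already accepts that dietary xanthines disturb this measurement, since that is the stated reason for the confinement rule. The rule is then lifted for one of the three occasions on which the same test is done. On Day 90 the caffeine-free interval before the tablet can be under two hours.

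Caffeine taken earlier has had longer to convert to paraxanthine, so residual dietary caffeine pushes PX/CAF up. Two things are at stake:

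- **Comparability over time.** The Day 90 ratio is compared with a Day 0 baseline, and read beside a Day 5 value, that were both obtained under a caffeine ban.
- **The arm contrast.** How far carry-over inflates the ratio depends on intake and on the rate of metabolism. The rate of metabolism is what the test is meant to compare between arms.

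Nothing in the schedule would detect the problem: there is no pre-tablet sample and no record of caffeine intake.

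**Working it through.** **1. Conditions at each test**

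- Day 0: admission procedures end by 18:30 on Day -2 (Table 8). The sample at 16:00–17:30 implies a tablet from 10:00. From 18:30 on Day -2 to 10:00 on Day 0 is 39.5 h.
- Day 5: the last caffeine is the Day 0 study tablet, so the gap is about 5 days. Counting all 7 days since admission would overlook that tablet.
- Day 90: caffeine at home is permitted until about 08:00. The 10-hour fast in 6.6.2.2 applies to the Day 31, 61 and 91 draws, not to this test.

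The documents give no half-life. For an assumed caffeine half-life h of 3.5 to 7 h, the fraction left after t hours is 2^(−t/h):

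- Pre-admission caffeine at the Day 0 tablet: at most 2^(−39.5/7) = 2%.
- A 07:30 cup at a 15:30 sample on Day 90: 2^(−8/3.5) = 21% to 2^(−8/7) = 45%.

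**2. Effect on the ratio**

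Assumptions, none from the documents: one compartment; 80% conversion of caffeine to paraxanthine; half-lives CAF/PX of 4/4 h in the cigarette arm (mCC) and 6/5 h in the THS arm; 100 mg per cup; tablet at 09:30, sample at 15:30. With k = ln 2/half-life, a dose D taken t hours before the sample contributes:

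- C = D·exp(−kc·t)
- P = 0.8·D·kc/(kp−kc)·[exp(−kc·t) − exp(−kp·t)], or 0.8·D·kc·t·exp(−kc·t) when kp = kc

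Tablet only (170 mg, t = 6):

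- mCC: C = 170 × 0.3536 = 60.1; P = 136 × 0.1733 × 6 × 0.3536 = 50.0; P/C = 0.83
- THS: C = 170 × 0.5 = 85.0; P = 136 × 5 × (0.5 − 0.4353) = 44.0; P/C = 0.52
- THS:mCC = 0.62

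Summing the dietary doses in the same way, with daily cups at 08:00, 13:00 and 18:00 on the preceding days and one at 07:30 on Day 90:

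| Scenario | mCC | THS | THS:mCC |
|---|---|---|---|
| No dietary caffeine | 0.83 | 0.52 | 0.62 |
| 07:30 cup only | 0.91 | 0.57 | 0.62 |
| Three cups daily plus 07:30 cup, both arms | 1.02 | 0.71 | 0.70 |
| Same, THS half the dose per cup | 1.02 | 0.64 | 0.63 |
| Same, mCC half the dose per cup | 0.94 | 0.71 | 0.75 |

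The level rises in every dietary scenario. The contrast need not move: the single morning cup adds about 10% in both arms and cancels.

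**3. Wider range**

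A second model with an absorption phase varied four quantities: THS caffeine half-life (3.5, 5, 7 h), mCC:THS enzyme activity (1.29, 1.41, 1.6), relative PX elimination (0.8, 1.0, 1.3) and the inducible share of PX clearance (0, 0.3, 0.6). Attenuation of the log-ratio was:

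- one 07:30 cup: −3% to +1%
- one cup the evening before: 2% to 18%
- four 100 mg cups daily in both arms: 0% to 50%, median 14%
- mCC 4 × 100 mg, THS 4 × 50 mg: −48% to +12% (negative means the contrast widens)
- THS 4 × 100 mg, mCC 4 × 50 mg: +7% to +113%

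**4. The plan's own CYP1A2 figure**

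Protocol 12.2 states 80% power for a difference of 0.631 with SD 0.564, one-sided 2.5%. At 40:40, the protocol's expected Day 90 per-protocol split, SE = 0.564 × √(1/40 + 1/40) = 0.126 and power = Φ(0.631/0.126 − 1.96) = 99.9%; at 80:40 it exceeds 99.9%. The stated 80% is not reproduced, and the discrepancy is conservative. At 40:40, a 20% smaller difference leaves 98.0% and a 50% smaller one leaves 70.6%. These inputs are for caffeine clearance rather than PX/CAF, so they are only indicative.

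**The case against.** The strongest case against runs as follows. The rule is the same in every arm. The ambulatory period is meant to reflect real-world use (Protocol 4.2), and 6.6.2.2 lifts the confinement restrictions knowingly. CYP1A2 is one of many secondary endpoints, and its objective is descriptive. Day 5 is caffeine-controlled, and Day 90 significance is looked at only if Day 5 is significant. On the protocol's own inputs, moderate attenuation would cost little power.

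Much of this stands, and it limits the weight of the point. Two parts do not answer it. An equal rule does not guarantee equal bias, because inflation depends on metabolic rate and on actual intake. The real-world rationale concerns product use, whereas the CYP1A2 test itself is still standardised for tablet, sampling time and pre-visit grapefruit. Neither argument restores comparability with Day 0 and Day 5.

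A reader might also infer that carry-over must shrink the THS–mCC difference. The documents do not support that. They give no caffeine intake, no kinetics and no information on whether intake differs between arms. In the calculations a lone morning cup leaves the contrast unchanged, and higher intake in the cigarette arm can widen it.

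**Conclusion.** The inconsistency between 6.6.2.1 and 6.6.2.2 is plain in the text and does not rest on a model. Day 90 PX/CAF is measured without the caffeine control applied at Day 0 and Day 5, so dietary carry-over raises its level and confounds change from baseline with diet.

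Bias in the THS–mCC contrast is possible, but its size and sign are not established. Under the first model's assumptions the true 0.62 appears anywhere from 0.62 to 0.75. Attenuation is plausible if habitual intake is similar in the two arms (about 0.70 in that model; 0% to 50% on the log scale across the grid). The figure of 0.70 is one scenario, not an estimate for this trial.

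The five primary biomarkers and the Day 5 CYP1A2 comparison are untouched.

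**What to change.** - **Protocol 6.6.2.1 and 6.6.2.2:** reconcile the two sections for the CYP1A2 test. Extend the existing pre-visit instruction before the Day 90 Visit to the items 6.6.2.1 already lists for CYP1A2: xanthine-containing food and drink, alcohol, broccoli, brussels sprouts and cauliflower.
- **Day 90 check-in:** record the time and amount of last xanthine intake. The schedule of events does not capture this, and the analysis below cannot be done without it.
- **SAP 12.6.2.4:** repeat the Day 90 analysis excluding subjects who report intake within that window, beside the existing repeat for medication.

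The cost is one sentence in the protocol and subject instructions, one question and one additional analysis. The downside is a short period without coffee or tea, with adherence known only by self-report. A pre-tablet PX/CAF sample would measure carry-over directly, for one more blood draw.

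The protocol's expected end date (31 August 2014) precedes SAP version 2.0 (07 November 2014). If the Day 90 visits are already complete, what remains is to state the limitation in the study report and not to read the Day 0 or Day 5 to Day 90 change as enzyme activity alone.

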6.7 Concomitant Medication

No medication should be taken during the study from the screening to the time of discharge on Day 91 without prior informing the Investigator. However, the Principal Investigator is responsible for the medical care of the subjects during their participation in this study. Any decisions regarding the prescribing of medication will be made in the best interests of the subject.

During the ambulatory period, subjects in the SA arm may use NRT on the judgment of the Investigator or on request of the subject. No medication supportive for smoking cessation other than NRT will be allowed in the study.

Concomitant use of NSAIDs and acetylsalicylic acid (including over-the counter products) is not allowed, as all of them could interfere with risk markers such as 11-DTX-B2. Paracetamol will be allowed at a daily total dose of up to 1500 mg. Any medication with an

Data and information contained in this document are considered to constitute trade secrets and confidential commercial information, and the legal protections provided to such trade secrets and confidential information are hereby claimed under the provisions of applicable law. No part of this document may be publicly disclosed without the written consent of Philip Morris Products S.A.

impact on the CYP1A2 and CYP2A6 metabolism (as prescription and over-the-counter products) as shown in Table 3 must be avoided.

If the use of a concomitant medication cannot be avoided for the subject's safety, it must be fully documented in the Source Document and transcribed into the eCRF (for details, see Section 7.4.5)..

The drugs and substances shown in Table 3 are a selection of drugs considered to have an impact on CYP1A2 and/or CYP2A6 activity (Chang et al., 1999, Ingelman-Sundberg et al., 1999, Lacy et al., 2007). Prior to database close, concomitant medication will be assessed according to their potential impact on CYP1A2 and CYP2A6 activity and potential impact on the study results.

Concomitant medication will first be assessed at Screening Visit. To be eligible for the study, any medication with impact on CYP1A2 and CYP2A6 metabolism must be discontinued at least 2 weeks prior to Admission to the clinic or for at least 5 half-lives (whichever is longer). They must not be used during the entire study until the time of discharge on Day 91 (completion of the study).

Medication containing estrogens (e.g. for contraception and for hormone replacement therapy), even though known to be CYP1A2 inhibitors, will be allowed in this study but must be documented on the eCRF.

**Table 3. Examples of Medications with effects on CYP1A2 and CYP2A6 activity**

Drug name	Substance Class
Fluoroquinolones, including ciprofloxacin and ofloxacin, nafcillin, rifampicin	Antibiotics
Fluvoxamine, fluoxetine, paroxetine, bupropion, duloxetine, amitriptyline, imipramine, sertraline, mirtazapine, citalopram, thioridazine	Antidepressant
Haloperidol, perphenazine, chlorpromazine, propoxyphene fluphenazine, clozapine, olanzapine	Neuroleptic
Phenobarbital, primidone, carbamazepine	Antiepileptic
Chlorquine, quinidine	Antirheumatic
Clotrimazole, terbinafine, fluconazole, ketoconazole, miconazole	Antimycotic
Erythromycin, ciprofloxacin, clarithromycin, norfloxacin	Antibiotic
Cimetidine, chlorpheniramine, diphenhydramine, ranitidine	H ₂ -receptor antagonist
Amiodarone, verapamil, mibepradil, mexiletine, propafenone, propanolol, lidocaine	Antiarrhythmic
Losartan, amlodipine, nifedipine,	Antihypertensive
Drospirenone, estrogens	Hormonal contraception, hormonal replacement therapy (estrogens)
Fluvastatin	Cholesterol-lowering agent
Theophylline	Antispasmodic pulmonological agent/Bronchodilator agent
Omeprazole, lansoprazole	Proton pump inhibitor
Interferon	Antiviral/Immunomodulating agent
Methoxsalen	Anti-psoriatic
Modafinil, diclofenac, rofecoxib	Analgesic
Insulin	Anti-diabetic
Sildenafil	Erectile dysfunction
Quinine	Leg cramps
St. John's Wort	Over-the-counter (herbal remedy) antidepressant
Psoralen	Anti-psoriatic (substance class Furocoumarins)
Pilocarpine	Cholinergic agonists (e.g., used for Glaucoma Therapy)

Data and information contained in this document are considered to constitute trade secrets and confidential commercial information, and the legal protections provided to such trade secrets and confidential information are hereby claimed under the provisions of applicable law. No part of this document may be publicly disclosed without the written consent of Philip Morris Products S.A.

Data source: Chang et al., 1999, Ingelman-Sundberg et al., 1999, Lacy et al., 2007. The list is not exhaustive.

7 STUDY PROCEDURES

Personnel performing study measurements or recordings must have the appropriate training fully documented. Quality and control measures have to be in place. An overview of all study procedures is shown in the Schedule of Events (Appendix 1). In this Section, only the expected/planned time points for the various measurements are described. As not all subjects can undergo a procedure at the same time, adequate time windows are given for each study procedure and each time point (see Section 9). Study collaborators will adhere to the site's Standard Operating Procedures (SOPs) for all activities. Appropriate medical advice will be provided to the subject in case of any medial findings requiring health care.

7.1 Informed Consent/Subject Information Sheet

Prior any study assessments is performed, the subject will be asked to provide his consent to participate to the study (ICF for study participation) (Section 1.3).

In addition to the ICF for study participation, the subject will be asked to provide his separate consent for two kinds of biobanking (Sections 1.3.2).

- ICF to the additional bio-banking of serum/plasma/urine samples for further measurements of BoExp and risk markers.
- ICF to the additional bio-banking of blood sample for further transcriptomics (pharmacogenomics) analysis.

The subject's participation in the study does not depend on their consent for both bio-banking for BoExp of exposure/risk markers and for pharmacogenomics analysis) will be separate to that for study participation. The three consents will be captured in the eCRF.

7.2 Advice on the Risk of Smoking/Smoking Cessation Advice and Debriefing

Each subject will be given advice on the risks of smoking six times during the study: at the Screening Visit, at Admission (Day -2), at Day 6, and at Day 30 Visit (Day 31), Day 60 Visit (Day 61), and Day 90 Visit (Day 91). This will take the form of a brief interview according to WHO recommendations (Raw et al., 2002). Details of the interview will be recorded in the Source Document File. Information on the risk of smoking will be given to the subjects on an individual basis during a face-to-face meeting between the subject and the Investigator, or dedignee and may additionally be given in a group session.

In addition to the smoking cessation advice, a debriefing of subjects will be done at each smoking cessation advice session to address any intended or unintended beliefs participants have about the candidate MRTP. The goal of the debriefing would be to help ensure that subjects exit the study with an accurate understanding of product risks, including an understanding that the candidate MRTP has not been demonstrated to be less harmful.

